3.1.1	Pharmacovigilance information	17
3.1.2	Adverse Event (AE).....	17
3.1.3	Adverse (drug) reaction (ADR)	17
3.1.4	Serious adverse (drug) reaction (SADR)	17
3.2	Responsibilities	18

3.2.1	Events to be reported	18
3.2.2	Responsibilities of the investigator	18
3.2.3	Responsibilities of the Sponsor/Marketing Authorisation Holder	19
4	Data management, quality management, statistics and reporting	19
4.1	Data management	19
4.2	Statistical analysis	19
4.3	Report preparation	19
5	Ethical considerations	20
6	Appendices	20
7	References	25

1 Introduction and aims

Introduction

A blood pressure (BP) lowering in the treatment of arterial hypertension (HTN) is associated with a reduction in the risk of cardiovascular mortality and the rate of complications (1,2). When prescribing antihypertensive drugs, the choice depends largely on the presence of concomitant diseases and associated conditions. The prevalence of HTN in patients with coronary artery disease (CAD) exceeds 80% (3). The BP control in patients with HTN and CAD is important, as the risk of recurring coronary events depends mostly on the BP level (4). For patients with HTN who have had a recent myocardial infarction (MI), it is recommended to use β_1 -adrenoceptor blocking agents and renin-angiotensin-aldosterone system (RAAS) inhibitors (5).

Monotherapy often does not contribute to achieving the target BP levels. The combination of two agents from any two classes of antihypertensive drugs is much more effective than monotherapy even at the maximum dose of the agent chosen for monotherapy (1,2). In addition to the higher efficacy, combination therapy provides a more potent organ-protective effect and has a better tolerance (by minimizing adverse effects and due to the ability to use lower doses) (2,6). The use of combination therapy increases patient adherence to treatment. A meta-analysis performed by Bangalore S et al. (2007) with the inclusion of data from 68 clinical trials assessing the single pill combinations (SPCs) and antihypertensive agents of various groups has demonstrated that antihypertensive SPCs increase treatment adherence by 24%, compared with free combinations in equivalent doses, and, therefore, provide better control of hypertension (7).

The studied efficacy and safety of perindopril and bisoprolol both in monotherapy and in free combination became the basis for the creation of Prestilol® medicine - a fixed combination of these active substances. Bisoprolol, a component of Prestilol®, is one of the long-acting β_1 -blockers with the highest selectivity. Bisoprolol reduces adrenergic stimulation of the heart muscle and pacemakers, which leads to a decrease in stroke volume and heart rate (HR), as well as the inhibition of renin secretion by the kidneys (3,6,8). In the BRIGHT study, 96.4% of 2161 patients with essential HTN showed significant reductions in systolic blood pressure (SBP), diastolic blood pressure (DBP) and HR after 12 weeks of bisoprolol monotherapy. Bisoprolol has demonstrated a marked BP-lowering effect and good tolerance. Moderate adverse events (AEs) were observed in only 1.9% of patients, and no serious AEs or drug withdrawals were reported (9).

Perindopril is a highly lipophilic angiotensin-converting-enzyme (ACE) inhibitor, which has a proven organ-protective effect and is able to improve outcome in HTN, CAD, and cerebrovascular diseases. Like other ACE inhibitors, perindopril inhibits the RAAS by reduction in the formation of angiotensin II. The latter is accompanied by a decrease in total peripheral vascular resistance, formation of aldosterone and, therefore, sodium and water retention, with a reduction in circulating blood volume (6). The EUROPA study assessed the efficacy of perindopril on the top of standard therapy with β_1 -blocker in CAD patients (67% of them had a history of MI, and one third had

concomitant HTN). Combination treatment with perindopril and β -blocker reduced the relative risk of the primary endpoint (cardiovascular death, nonfatal MI, and resuscitated cardiac arrest) by 24% compared with β -blocker monotherapy (HR, 0.76; 95% CI, 0.64-0.91; $P = 0.002$). Addition of perindopril also reduced fatal or nonfatal MI by 28% (HR, 0.72; 95% CI, 0.59-0.88; $P = 0.001$) and hospitalization for heart failure by 45% (HR, 0.55; 95% CI, 0.33-0.93; $P = 0.025$) (10,11). There are other published data from several studies of the bisoprolol/perindopril SPC efficacy in hypertensive patients with CAD.

Korenova O.Yu. et al. (2019) evaluated the efficacy of bisoprolol/perindopril SPC in patients with recent acute coronary syndrome (ACS) who underwent endovascular coronary intervention. The study has demonstrated an efficient and optimal in time (within the first 4 weeks) achievement of target levels of SBP, DBP and HR, as well as persistence of the effects after 12 weeks of treatment. Clinical benefits of bisoprolol/perindopril SPC included a significant reduction in the severity and rates of manifestations of chronic heart failure and/or angina pectoris (3).

The data of PRESTOL (2019) study examined the efficacy of bisoprolol/perindopril SPC in 2394 hypertensive patients with CAD and showed significant reductions in HR (target HR \leq 70 beats per minute was achieved in 84.9% of patients) and BP (target BP \leq 140/90 mm Hg was achieved in 86.9% of patients). The treatment was associated with a reduction in the number of angina attacks (from 4.4 to 2.6 per week) and an improvement in the treatment adherence level (up to 66.5% of patients) (8).

SPC of bisoprolol/perindopril with several doses of 5/5, 5/10, and 10/10 mg in one tablet makes possible to individualize therapy and increase treatment compliance, while breakable tablets of 5/5, 5/10 mg combinations provide additional options for dose titration (12).

Aim

This non-interventional, ambispective study was aimed at describing effectiveness, safety, and tolerability of bisoprolol and perindopril SPC in patients with HTN and previous myocardial infarction treated with the SPC for 12 weeks in the real clinical practice. SPC will be used according to the approved instruction for medical use of the medicine.

Primary objectives

- To describe antihypertensive effectiveness (SBP and DBP reduction) of bisoprolol/perindopril SPC in hypertensive patients with previous MI at week 12 of prospective observation.

Secondary objectives

- To describe antianginal effectiveness of bisoprolol/perindopril SPC in hypertensive patients with a history of MI at week 12 of prospective observation.
- To describe a proportion of patients achieving target systolic and diastolic BP levels among hypertensive patients with previous MI during 12 weeks of prospective observation with bisoprolol/perindopril SPC according to the age (as stated in the guidelines “2”)

- To describe mean change in resting HR from BL among study patients at week 12 of prospective observation.
- To describe a proportion of patients who achieved resting HR less than 60 bpm at week 12 of prospective observation.
- To estimate association between the resting HR and achievement of target level of BP at week 12 of prospective observation.
- To describe adherence to the treatment with bisoprolol / perindopril in hypertensive patients with previous MI during the prospective observational period of 12 weeks.
- To describe the tolerability of treatment with bisoprolol / perindopril in hypertensive patients with previous MI during 12 week prospective observation.

Outcome measures

Primary outcome measure:

- Change in the mean systolic and diastolic BP levels at week 12 of prospective observation compared to baseline among patients included in the study.

Secondary outcome measures:

- Change in mean systolic and diastolic BP levels at week 4 of prospective observation compared with baseline.
- Change in number of angina attacks per week at week 4 of prospective observation compared with baseline.
- Change in number of angina attacks per week at week 12 of prospective observation compared with baseline.
- Proportion of patients who were taking lipid lowering therapy (LLT) at week 12 of prospective observation.
- Proportion of patients receiving LLT who achieved target levels of LDL C at week 12 of prospective observation.
- Proportion of patients who achieved SBP \leq 140 mm Hg and DBP \leq 90 mm Hg at week 4 of prospective observation.
- Proportion of patients who achieved SBP \leq 140 mm Hg and DBP \leq 90 mm Hg at week 12 of prospective observation.
- Proportion of patients younger than 65 who achieved SBP \leq 130 mm Hg and DBP \leq 80 mm Hg at week 4 of prospective observation .
- Proportion of patients younger than 65 who achieved SBP \leq 130 mm Hg and DBP \leq 80 mm Hg at week 12 of prospective observation.
- Proportion of patients older than 65 years who achieved SBP \leq 140 mm Hg and DBP \leq 90 mm Hg at week 4 of prospective observation.

- Proportion of patients older than 65 years who achieved SBP≤140 mm Hg and DBP ≤90 mm Hg at week 12 of prospective observation .
- Changes in the mean heart rate (HR) at week 4 of prospective observation compared with baseline.
- Changes in the mean heart rate (HR) at week 12 of prospective observation compared with baseline.
- Proportion of patients who achieved target level of resting HR (55-60 bpm) at week 4 of prospective observation.
- Proportion of patients who achieved target level of resting HR (55-60 bpm) at week 12 of prospective observation.
- Correlation between the resting HR values stratified by groups and achievement of BP targets at week 12 of prospective observation .
- Proportions of patients with high, medium or low adherence to the treatment with SPC of bisoprolol/perindopril, assessed by MMAS-8 self-reporting questionnaire at week 4 of prospective observation.
- Proportions of patients with high, medium or low adherence to the treatment with SPC of bisoprolol/perindopril, assessed by MMAS-8 self-reporting questionnaire at week 12 of prospective observation.
- Incidence rate of adverse events/ adverse drug reactions and special situations during 12 week observational period of the study.

2 Methods and documentation

Study design and definitions

This is a multi-centre, observational, incomparative, ambispective study, which will retrospectively and prospectively collect clinical and socio-demographic data from medical records of patients with HTN and previous MI initiated with bisoprolol/perindopril SPC in real clinical settings.

Baseline data will be collected retrospectively from medical records of patients with HTN and a history of MI. Baseline data are defined as clinical parameters of interest available in medical records at the nearest date before or at the date of the initiation of SPC with Bisoprolol/ Perindopril.

To be included in the study for further prospective observation a patient should have been administered bisoprolol/ perindopril SPC within first three months before the Index Date. (*Fig.1*).

The Index date is a date when a decision to include a patient in the study for further 12 week prospective observation made by a treating physician after evaluation of recorded data to confirm patient's eligibility for the study.

Therefore, criteria for non-inclusion or inclusion of patients in the study are to be retrospectively evaluated by the treating physician using recorded clinical data available from medical records. Once a treating physician makes decision to include a patient in the study and, in particular, on the prospective observation for 3 months, a visit 0 (inclusion visit) to the clinic for obtaining signed patient's consent to participate in the study should be appointed and made within 1 month from the Index Date.

Retrospective screening and evaluation of patient's eligibility to inclusion/ exclusion criteria for entering the study allows mitigating a potential risk of deliberative medicine administration within the observational program. Such studies are carried out in case of observational programs when the studied drug is administered in line with indications according to the instruction for its medical use.

Several multicenter, non-interventional, open, incomparable studies have been performed with bisoprolol/perindopril SPC in patients with HTN and coronary heart disease (3,8,13,14). A total of 70 general practitioners and cardiologists from primary care facilities will participate in the program. Each doctor will include about 7-8 patients. In total, it is planned to include at least 500 patients.

Calculation of the sample size

As the present research has an exploratory nature, the study is not intended to prove any hypothesis. In this case, a formal calculation of the sample size is not performed. Moreover, all statistical tests will be performed at a level of statistical significance of 0.05 and a power of 80%.

Given that the study will include patients with any grade HTN, the variability of SBP and DBP levels may be high enough. However, assuming that standard deviations (SDs) at baseline does not exceed 50 mm Hg, a sample of 500 patients will allow achieving a statistically significant difference in BP reduction after 3 months of treatment with bisoprolol/perindopril SPC compared with baseline levels, providing it is 6.3 mm Hg or more.

This non-interventional study has an exploratory nature, so the sample size is not a strict parameter and is recommendatory in nature.

Therefore, in order to obtain a representative population of patients with this particular disease and taking into account the practical aspects of conducting research in daily everyday routine practice, the total sample should consist of at least 500 patients.

Selection of doctors

A total of 70 general practitioners and outpatient cardiologists will participate in this non-interventional study.

Selection of patients

Inclusion criteria

1. Age from 18 to 79 years.
2. Signed informed consent to participate in the study.
3. Stable arterial hypertension with concomitant stable angina pectoris of class I-III according to the Canadian Cardiovascular Society (CCS) classification and a history of myocardial infarction not earlier than 3 months before inclusion in the study
4. Bisoprolol/perindopril SPC prescription 1-3 months before screening
5. Bisoprolol/perindopril SPC prescription in accordance with Russian SmPC, based on necessity in treatment with bisoprolol/perindopril SPC and separated from the decision to include the patient in the study
6. Clinical parameters of interest (Resting HR; SBP and DBP; frequency of angina attacks per week) are available in medical records for the nearest date before or at the date of the initiation of SPC with Bisoprolol/ Perindopril.

Non-inclusion criteria

1. Hypersensitivity to bisoprolol, perindopril, excipients of the medicine, or other ACE inhibitors.
2. Any contraindication for bisoprolol/perindopril's SPC according to the instruction for medical use
3. CAD, angina pectoris of functional class IV according to the CCS classification (Appendix 1).
4. Chronic heart failure of class III-IV according to the New York Heart Association (NYHA) functional classification of heart failure (Appendix 3).
5. Cerebrovascular diseases (ischemic, haemorrhagic stroke, or transient ischemic attack) within the past 6 months prior to inclusion in the study.
6. A history of revascularization procedure within 3 months prior to inclusion in the study.
7. Hypertrophic obstructive cardiomyopathy.
8. Office BP \geq 180/110 mm Hg on treatment
9. Type 1 diabetes mellitus and decompensated type 2 diabetes mellitus.
10. Bradycardia with a heart rate of less than 60 beats per minute.
11. Atrioventricular block (II-III degree), sinoatrial block, or sick sinus syndrome.
12. Severe bronchial asthma or severe chronic obstructive pulmonary disease.
13. Arterial hypotension (BP less than 100/70 mm Hg).
14. Pregnancy, breastfeeding.
15. Secondary hypertension.
16. Severe decompensated diseases of organs and systems requiring continuous treatment.
17. Current participation in another clinical trial and within 30 days prior to signing informed consent.

Treatment during the study

Treatment with the studied drug

bisoprolol 5 mg + perindopril 5 mg once daily
bisoprolol 5 mg + perindopril 10 mg once daily
bisoprolol 10 mg + perindopril 5 mg once daily
bisoprolol 10 mg + perindopril 10 mg once daily

A minimum dosage may also be prescribed:

bisoprolol 2.5 mg + perindopril 2.5 mg 1 time per day (1/2 tablet of bisoprolol 5 mg + perindopril 5 mg)

If the dose adjustment is required, the treating physician can correct the dosage of the drug at any time after the treatment start. The decision on the need to correct the dosage lies upon the treating physician.

In renal failure, it is necessary to adjust the dose depending on the degree of impaired renal function (creatinine clearance).

Concomitant drugs

Due to the non-interventional design of the study, it is allowed to use any concomitant treatment or drugs if it is considered necessary by the treating physician and not contraindicated according to the approved instruction for use. This treatment will be appropriately reflected in the study documentation.

Duration of non-interventional study

It is planned to complete enrolment of patients in this non-intervention study within 6 month.

Follow-up period for each patient will be 3 months.

First patient in is scheduled for Q1 2021

Last patient in is scheduled for Q3 2021

Last patient last visit Q4 2021

Data base lock is scheduled for Q1 2022

Statistical analysis is scheduled for Q2 2022

Clinical study report is scheduled for Q2 2022

Documentation during the non-intervention study

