3.2.3 Responsibilities of the Sponsor/Marketing Authorisation Holder

Independently of the regulatory obligations of investigator, the sponsor/marketing authorisation holder (MAH) must report the pharmacovigilance data to the appropriate authorities in accordance with the Good Pharmacovigilance Practice and local regulations.

Cases of adverse event are considered to be closed when the patient has recovered or his/her condition was stabilised, providing that the available data are sufficiently detailed for adequate medical analysis of the case.

4 Data management, quality management, statistics and reporting

Data management

Data collection in this study is carried out using documentation forms. Centralized data entry will be carried out by a responsible professional subcontractor for statistical analyses after receiving documentation forms. Statistical analysis of the data and the creation of the final statistical report on the study will also be carried out by the responsible professional subcontractor for statistical analyses. The consistency of reported AE data will be ensured by reconciling the project database with the Servier drug safety database. Discrepancies will be resolved by mutual agreement between both parties (Servier and professional subcontractor for statistical analyses).

Statistical analysis

Due to the non-interventional nature of this study, statistical analysis will be carried out in descriptive and exploratory forms. All parameters will be analysed using descriptive statistics. For each parameter, the following will be specified: number of patients, mean value, standard error, minimum and maximum values, or proportion of each category. All composite endpoints will be listed and presented in visual form as graphs and in tables of parameters and their frequencies. For categorical variables, absolute values and rates in per cents be calculated. The calculations of relative rates will include only patients in whom values of the corresponding variables will be available.

All reports of adverse drug reactions (ARDs), adverse events (AEs), serious ADR/AE, and special situations will be encoded, and the results will be listed and classified according to the System-Organ-Classes (SOCs).

Accepted level of significance

In all tests, a significance level of 0.05 will be used, and 2-sided statistical tests will be carried out.

Report preparation

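### The HR–BP outcome groups resting HR and leaves the groups, the measure and the BP target open; a logistic model on continuous HR would be more precise

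*Combined protocol and SAP*

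**What the plan says.** Section 1, Secondary objectives, sets the aim: "To estimate association between the resting HR and achievement of target level of BP at week 12 of prospective observation". The matching entry under Secondary outcome measures is "Correlation between the resting HR values stratified by groups and achievement of BP targets at week 12 of prospective observation".

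That entry does not define the groups, the cut-points or the coefficient. It also does not say which BP target counts. The same list offers two: at most 140/90 mm Hg for all patients, or an age-specific target (at most 130/80 below 65 years, at most 140/90 above). HR thresholds appear elsewhere in section 1 (below 60 bpm in one objective, a band of 55 to 60 bpm in two outcomes), but neither is tied to this outcome.

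Section 4, Statistical analysis, says that "statistical analysis will be carried out in descriptive and exploratory forms" and that "All parameters will be analysed using descriptive statistics". It lists counts, means, standard errors, ranges and proportions. Under Accepted level of significance, "a significance level of 0.05 will be used, and 2-sided statistical tests will be carried out". No correlation method, regression model or covariate is named, so adjustment is neither planned nor excluded. Section 2, Calculation of the sample size, describes the study as exploratory, with no hypothesis to prove.

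**The concern.** Resting HR is measured as a number. If it is collapsed into categories before being related to target attainment, the variation within each category is thrown away and the estimate is less precise than the data allow. A correlation with a binary outcome also gives no effect in usable units, such as the change in odds of reaching target per 5 bpm.

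The second problem is that too much is left open. With tests at 0.05 foreseen, but the HR groups, the measure of association and the BP target all unstated, several analyses would fit the wording. The choice among them could be made after the data are seen. At stake is the quality of one secondary, descriptive result. The primary outcome is not affected.

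**Working it through.** **1. The plan's own figure.** None is given for this outcome. The only precision statement concerns the primary BP change: "assuming that standard deviations (SDs) at baseline does not exceed 50 mm Hg", 500 patients, a reduction detectable "providing it is 6.3 mm Hg or more", where "all statistical tests will be performed at a level of statistical significance of 0.05 and a power of 80" per cent. Check: SD × (z0.975 + z0.80)/√n = 50 × 2.8016/√500 = 140.08/22.361 = 6.26, which rounds to 6.3 mm Hg. It reproduces if 50 is taken as the SD of the change. It says nothing about the HR–BP association, so the rest relies on stated assumptions.

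**2. Information kept by equal groups.** Assume a normal HR and a linear trend. The share kept is Σ pⱼmⱼ², where pⱼ is the proportion in group j and mⱼ the mean standardised HR in it.

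- Two groups: means ±0.3989/0.5 = ±0.798; share 0.798² = 0.637; 500 × 0.637 ≈ 318.
- Three groups: cuts ±0.4307, density 0.3636, outer means ±0.3636 × 3 = ±1.091, middle 0; share (2/3) × 1.091² = 0.793; about 397.
- Four groups: outer means ±0.3178/0.25 = ±1.271, inner ±(0.3989 − 0.3178)/0.25 ≈ ±0.325; share 0.5 × (1.616 + 0.105) = 0.861; about 430.

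**3. A single cut at 60 bpm.** The documents give no HR mean or SD for week 12, so these are varied. With c = (60 − mean)/SD, density φ(c) and p the proportion below 60, the share is φ(c)²/[p(1 − p)]. For mean 68 and SD 8: c = −1, 0.2420²/(0.1587 × 0.8413) = 0.0586/0.1335 = 0.439.

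| Assumed mean, SD (bpm) | Share kept |
|---|---|
| 62, 10 | 0.627 |
| 65, 8 | 0.552 |
| 68, 8 | 0.439 |
| 72, 6 | 0.131 |

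Over means of 62 to 72 and SDs of 6 to 10, the range is 13% to 63%. Two cuts, at 60 and 70 bpm, keep 66% to 81% over the same grid.

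**4. Detectable correlation at 80% power.** By Fisher's z, as an approximation, r = tanh[2.8016/√(n − 3)]. This gives 0.125 for n = 500 (continuous HR), 0.140 for n ≈ 397 (three equal groups) and 0.156 for n ≈ 318 (median split).

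**5. Power, by illustrative simulation.** In 600 runs of 500 patients with one assumed monotone HR effect, power was 79% with continuous HR, 63% with groups cut at 60 and 70 (chi-square) and 51% with a single cut at 60. Part of the three-group loss comes from a chi-square test that ignores the order of the groups.

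**6. Would adjustment matter?** In 500 runs per setting, HR had no effect given the covariates, while baseline BP, age and dose were linked to both HR and BP with assumed strengths. The table shows the percentage of runs significant at 0.05.

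| Assumed links | Crude, continuous | Crude, three groups | Adjusted | Crude OR per 8 bpm |
|---|---|---|---|---|
| None | 6 | 4 | 6 | 1.00 |
| Moderate | 26 | 16 | 5 | 0.87 |
| Strong | 66 | 43 | 4 | 0.79 |

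Crude and adjusted answers can therefore differ. Whether they do here depends on link strengths that the documents do not give. The adjusted model included dose, which in the simulation did not react to on-treatment HR or BP.

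**The case against.** The best defence is that the study is descriptive and the objective asks only for an association. A correlation is a measure of association, and a crude one is a legitimate quantity to report. That stands. A reader might infer that the planned analysis cannot answer its objective. The documents do not support this: it can, with less precision and on a less useful scale.

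A reader might also infer that the plan prescribes an unadjusted analysis whose result would mostly reflect dose, age and starting BP. That goes too far as well. The plan is silent on adjustment, and the strength of any shared causes is unknown. Confounding would be an error only if the result were presented as an independent or causal effect of HR, which the protocol nowhere claims.

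Other points stand in part:

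- The wording about groups could mean HR values within patient groups, such as age groups. The precision loss would then not arise. HR categories are the more natural reading, and the ambiguity itself needs removing.
- With three or more equal groups the practical loss is modest (step 4). It becomes large only with few or off-centre cuts.
- The HR target is a band, so the relation may not be linear, and a table by group could show a shape that a single slope would miss. This is a reason to keep the table and to check the form of the model.
- Section 2 lets the treating physician change the dose at any time. A later dose may be a response to BP or HR, and adjusting for it can add bias.

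**Conclusion.** The point holds as a low-priority improvement. The HR groups, the measure of association and the BP target are not fixed in advance, and grouping, on its natural reading, gives up precision. Under a normal HR and a linear trend the loss is about 14% to 36% of the information for four down to two equal groups, and 37% to 87% for a single cut at 60 bpm over the assumed HR distributions. These sizes rest on assumptions, because the plan states neither cut-points nor an HR distribution. The simulated power and rejection rates are illustrations only. No sample-size figure changes.

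**What to change.** Name the BP target for this outcome in advance. Make the main analysis a logistic regression of week-12 target attainment on continuous week-12 resting HR, with a check for non-linearity (for example a spline). Report the odds ratio per 5 bpm with its 95% CI, using standard errors clustered by doctor (70 doctors, about 7 to 8 patients each).

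Give the crude estimate first, since the objective is descriptive. Beside it give an estimate adjusted for age group and baseline SBP, DBP and HR, with a statement that it is not a causal effect of HR. Use SPC dose only in a sensitivity analysis, taken at a stated visit such as V0. Keep the table by HR group, with stated cut-points, as description.

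The data are already to be collected. Baseline HR and BP are an inclusion requirement, and Table 1 and the visit lists in section 2.7.4 cover demographics, dose status and final-visit vital signs. The cost is a small amendment to one secondary outcome line in the protocol, matching analysis text, and slightly more analysis.

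### No rule places the baseline BP, heart rate and angina record after the qualifying infarct, so some changes from baseline can include infarct and recovery effects

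*Combined protocol and SAP*

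**What the plan says.** **Baseline.** Section 2, Study design and definitions, takes as baseline the values that are "available in medical records at the nearest date before or at the date of the initiation of SPC". Inclusion criterion 6 repeats the rule for resting heart rate, BP and weekly angina attacks, which must be such that they "are available in medical records for the nearest date before or at the date of the initiation of SPC with Bisoprolol/ Perindopril". Table 1 in 2.7.4 uses the same anchor. None of the three mentions the MI or limits how far back the record may lie.

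**MI.** Inclusion criterion 3 asks for "a history of myocardial infarction not earlier than 3 months before inclusion in the study". The anchor is inclusion, not the baseline record and not SPC start.

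**SPC start.** Inclusion criterion 4: "Bisoprolol/perindopril SPC prescription 1-3 months before screening". The inclusion visit (V0) "should be appointed and made within 1 month from the Index Date".

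**Order of MI and SPC.** This is only implied, by the description of the cohort as "patients with HTN and previous MI initiated with bisoprolol/perindopril SPC in real clinical settings".

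**Use of the baseline.** The primary outcome is the week-12 change in systolic and diastolic BP from this baseline, and the primary objective presents it as antihypertensive effectiveness of the SPC. The heart rate and angina changes are secondary outcomes on the same baseline. There is no comparator. The Statistical analysis text in Section 4 has no restriction, adjustment or sensitivity analysis for the date of the baseline record.

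**The concern.** Three dates matter for each patient: the MI, the baseline record and SPC start. The plan orders the baseline record against SPC start and leaves both unordered against the MI, apart from the implied order of MI and SPC. A reading taken during the acute infarct therefore meets the baseline definition, and so in some circumstances does one taken before it.

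For such a patient, the change to week 12 spans the infarct or its acute phase, the acute care, the recovery and any other drugs started then, as well as the SPC. With a single group, nothing in the data separates these. The direction need not be the same for BP, heart rate and angina. A pre-MI value also does not describe a hypertensive patient with previous MI, which is the population named in the objectives. A larger sample does not remove a shift of this kind.

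**Working it through.** **1. The plan's own figure.** Calculation of the sample size gives N = 500, SD 50 mm Hg, alpha 0.05, power 80% and a detectable reduction of 6.3 mm Hg. Section 4 makes the tests two-sided. One-sample formula on the change: (1.960 + 0.842) x 50 / √500 = 2.802 x 2.236 = 6.26, which rounds to 6.3. It reproduces if 50 is read as the SD of the change. The standard error of the mean change is then 50 / √500 = 2.24 mm Hg. The present point does not alter this figure.

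**2. Where the MI can fall relative to SPC start.** I treat screening and the Index Date as the same moment. SPC start is then 1-3 months before inclusion if inclusion means the Index Date, and 1-4 months before if it means V0 (up to 1 month later). Criterion 3 can be read literally (MI 0-3 months before inclusion) or as meaning at least 3 months before.

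| Criterion 3 | Inclusion means | Earliest MI relative to SPC start | Latest MI relative to SPC start |
|---|---|---|---|
| 0-3 months | Index Date | 3 - 1 = 2 months before | 3 - 0 = 3 months after |
| 0-3 months | V0 | 3 - 1 = 2 months before | 4 - 0 = 4 months after |
| at least 3 months | Index Date | no limit | 3 - 3 = 0, at SPC start |
| at least 3 months | V0 | no limit | 4 - 3 = 1 month after |

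In every row the MI can be close to SPC start. In three of the four it can follow it, and the baseline is then necessarily earlier than the MI.

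**3. What the nearest-record rule then selects.**
- MI before SPC start, with a settled record in between: the baseline is post-MI and there is no problem.
- MI before SPC start, with only an acute in-hospital record in between: that reading can be the baseline.
- MI before SPC start, with no qualifying record in between: the baseline is pre-MI.
- MI after SPC start: the baseline is pre-MI.

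**4. Possible size (assumed inputs).** Let q be the share with a pre- or peri-MI baseline, and d the BP shift in those patients for reasons other than the SPC. The mean change is off by q x d. The last column is the chance of p < 0.05 when the SPC effect is zero, with standard error 2.24.

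| q | d (mm Hg) | q x d (mm Hg) | Chance of p < 0.05 |
|---|---|---|---|
| 10% | 5 | 0.5 | 5.6% |
| 20% | 10 | 2.0 | 14.5% |
| 40% | 15 | 6.0 | 76.5% |

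For the shift alone to reach 6.3 mm Hg, d must be 6.3 / 0.10 = 63 at q = 10%, or 6.3 / 0.20 = 31.5 at q = 20%.

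**The case against.** The strongest reply is that the rule asks for the nearest record in the medical records and is not limited to outpatient visits. A patient started on the SPC at discharge will ordinarily have a reading from around discharge, so a pre-MI value needs an empty interval between MI and SPC start, or an MI after SPC start. This stands. A reader might infer that pre-MI baselines are routine, and the text does not support that.

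Criterion 6 also asks for a weekly angina count, which fits an acute in-hospital record poorly. This cuts both ways: it makes an acute baseline less likely, but it can push the search back to a visit before the infarct. The exclusion of revascularisation within 3 months and the requirement of stable hypertension and stable angina narrow the group. They do not date the baseline record. If the MI must be at least 3 months old, there is no upper limit on its age, and patients with old infarcts will mostly be unaffected.

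The Introduction recommends beta-blockers and RAAS inhibitors after a recent MI. A reader might infer that the SPC is usually started close to the infarct, but the plan does not say when it is started.

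Finally, the study is exploratory and descriptive and allows any concomitant drug, so attribution to the SPC is limited already. That is true, and it makes the harm incremental. It does not make a change measured across the infarct a description of SPC effectiveness.

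**Conclusion.** The gap is real under either reading of criterion 3: no rule places the baseline record after the qualifying MI, and no planned analysis deals with records that are not. For the patients concerned, the primary BP change and the heart rate and angina changes include infarct and recovery effects.

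How many patients this touches, how far their values shift and in which direction are not in the documents. The 0.5-6 mm Hg range rests wholly on assumed q and d, and its upper end needs both at their maximum. A reader might infer that the primary result is biased by about the detectable difference, or biased in favour of the SPC. Neither follows, and the effect may be negligible. The 6.3 mm Hg comparator itself rests on an assumed SD ceiling and is not a clinical threshold.

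This is a cheap improvement to what the study can conclude, not a flaw that invalidates it.

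**What to change.** 1. Record in the CRF the dates of the MI and of discharge from it, of each baseline value, and of SPC start. The CRF is not among the documents, so some of these may already be collected; Table 1 lists medical history at V0.
2. Report the distribution of the gaps between MI, baseline record and SPC start.
3. Keep all included patients. Pre-specify in Statistical analysis that the primary systolic and diastolic change, and the heart rate and angina changes, are also reported for patients whose baseline is dated after MI discharge, with the others shown separately.
4. State that the change will be attributed to the SPC only if the two sets of results agree. Judge agreement from the estimates and their confidence intervals. With 400 and 100 patients and SD 50, the difference between groups has standard error 50 x √(1/400 + 1/100) = 5.59 mm Hg, so a non-significant difference would show little. Agreement removes this one explanation, not the other limits of a single-group design.
5. Reconcile criterion 3 with the study design text that describes the MI as preceding SPC initiation, and say whether inclusion means the Index Date or V0.

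Do not add an entry criterion requiring a post-discharge baseline. Patients who start the SPC at discharge could not ordinarily meet it, so it would remove them without correcting their baseline.

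The cost is two or three more dates per patient and a smaller N in the restricted analysis. If 20% fall outside it, N = 400 and the standard error rises from 2.24 to 50 / √400 = 2.50 mm Hg; at 40%, N = 300 and it is 50 / √300 = 2.89. Planned N, alpha and power are unchanged.
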